## PROTOCOL SYNOPSIS

**Title:** **PREEMPT CRC: Prevention of Colorectal Cancer Through Multiomics Blood Testing**

**Background:** Currently, there are different methods available for colorectal cancer (CRC) screening, each with their own strengths and weaknesses. Colonoscopy (CS) is highly sensitive, but is inconvenient and invasive, and therefore less appealing. Non-invasive, stool-based approaches are more convenient, but are also less accurate (especially for early-stage disease and precancerous polyps), and require manipulating stools, which can be unpleasant. Consequently, despite being widely recommended, approximately one-third of age-eligible adults remain unscreened for CRC, and cancer is often detected too late for successful treatment. Freenome has developed a blood-based multiomics screening test to detect advanced colorectal neoplasia (ACN) that applies the power of artificial intelligence (AI) and machine learning (ML) to multiomics plasma profiling. In a prospective, multi-center clinical study, Freenome's test demonstrated high sensitivity (94%) and high specificity (94%) for early-stage (I/II) CRC. The availability of such a highly accurate blood-based test should help overcome some of the challenges with existing CRC screening methods. This study aims to validate the performance of Freenome's test and support its regulatory approval.

**Sites:** Approximately 130 sites internationally.

**Population:** Subjects between the ages of 45 and 85 (inclusive) within 30 days of enrollment who are at average risk of developing CRC. Enrollment will be stopped when a sufficient number of evaluable CRC cases have been diagnosed among the study population. Approximately 25,000 subjects will be enrolled, and an effort will be made to enroll approximately 70% of subjects in the 65-85 age group.

**Study Design:** This is an international multi-center validation study. Subjects who meet eligibility criteria, provide informed consent, and provide a blood sample will be enrolled in the study. The blood collection must be done prior to undergoing bowel preparation for standard of care (SOC)

screening CS. Subjects will have the option to have blood collection done either at the study site or via mobile phlebotomy services, in which case the subject can have blood collected in their home or other location of preference. Subjects will have up to 50 mL of blood collected. De-identified blood specimens will be sent to Freenome or a designee for processing, testing, and storage. Specimens will be tested by laboratory personnel blinded to the results of the SOC screening CS. Subjects will undergo a SOC screening CS within 90 days of the blood collection. Subjects and their health care providers will be blinded to the results of Freenome's test, which will not be used in clinical management.

**Objectives:**

Primary:

- The primary objectives of this study are to determine the sensitivity (Sn) and specificity (Sp) of Freenome's test for colorectal adenocarcinoma using screening CS with histopathology as the reference method

Secondary:

- To evaluate the negative predictive value (NPV) of Freenome's test for CRC detection
- To evaluate the positive predictive value (PPV) of Freenome's test for CRC detection
- To evaluate the Sn of Freenome's test for advanced adenoma (AA)

**Inclusion Criteria:**

To be enrolled in this study, subjects must meet all of the following criteria:

1. 45-85 years of age (inclusive) within 30 days of enrollment (target  $\geq 70\%$  of subjects to be 65-85)
2. Willing to undergo a SOC screening CS within 90 days of blood collection
3. Considered by a physician or healthcare provider to be “average risk” for CRC

4. Able and willing to provide blood samples per protocol
5. Able to comprehend and willing to sign and date the informed consent document(s)

**Exclusion Criteria:** Subjects will be excluded from enrolling into the study if any of the following are met:

1. Family history
  - 1.1. At least 1 first-degree relative diagnosed with CRC before the age of 60 (Note: First-degree relatives include parents, siblings and offspring.)
  - 1.2. At least 2 first-degree relatives diagnosed with CRC at any age
  - 1.3. Known hereditary gastrointestinal cancer syndrome including but not limited to the following:
    - 1.3.1. Hereditary non-polyposis CRC syndrome (HNPCC) or Lynch Syndrome
    - 1.3.2. Familial adenomatous polyposis (FAP)
    - 1.3.3. Cowden's Syndrome
    - 1.3.4. Juvenile Polyposis Syndrome
    - 1.3.5. MUTYH-associated Polyposis
    - 1.3.6. Peutz-Jeghers Syndrome
    - 1.3.7. Serrated Polyposis Syndrome
2. Personal history
  - 2.1. CRC or colorectal adenoma
  - 2.2. History of any malignancy (except for non-melanoma skin cancer) at the time of enrollment, and for the 5 years preceding enrollment

- 2.3. Inflammatory bowel disease (IBD), including chronic ulcerative colitis (CUC) and Crohn's disease (CD)
- 2.4. Total colonic resection
- 2.5. Cystic fibrosis (CF)
- 2.6. CS in the 9 years preceding enrollment with the exception of an incomplete colonoscopy, or for a poor or inadequate bowel prep
- 2.7. Sigmoidoscopy or CT colonography in the 4 years preceding enrollment
- 2.8. Stool DNA testing in the 2 years preceding enrollment
- 2.9. Fecal occult blood testing (FOBT) or fecal immunochemical testing (FIT) in the 6 months preceding enrollment
- 2.10. Requiring an immediate or emergent colonoscopy for the investigation of symptoms
- 2.11. Solid organ or bone marrow transplantation
- 2.12. Blood product transfusion in the 120 days preceding enrollment
- 2.13. Any trauma or surgery requiring overnight inpatient hospitalization in the 30 days preceding enrollment
3. A medical condition which, in the opinion of the Investigator, should preclude enrollment in the study
4. Participated in or currently participating in a clinical research study in which an experimental medication has been administered during the 60 days up to and including the date of providing informed consent or may be administered through the time of the CS
5. Known to be pregnant

**LIST OF ABBREVIATIONS**

AA	Advanced Adenoma
ACN	Advanced Colorectal Neoplasia
ACS	American Cancer Society
AE	Adverse Event
AI	Artificial Intelligence
AUC	Area under the curve
CD	Crohn's Disease
CFR	Code of Federal Regulations
CIOMS	Council for International Organizations of Medical Sciences
CI	Confidence Interval
CRC	Colorectal Cancer
CRO	Contract Research Organization
CS	Colonoscopy
CTA	Clinical Trial Agreement
CUC	Chronic Ulcerative Colitis
DMARD	Disease-modifying anti-rheumatic drugs
DMC	Data Monitoring Committee
eCRF	Electronic Case Report Form
EDC	Electronic Data Capture

FAP	Familial Adenomatous Polyposis
FAS	Full Analysis Set
FDA	Food and Drug Administration
FIT	Fecal Immunochemical Testing
FOBT	Fecal Occult Blood Testing
GCP	Good Clinical Practice
HNPPCC	Hereditary Non-Polyposis Colorectal Cancer
IBD	Inflammatory Bowel Disease
ICH	International Conference on Harmonization
ID	Identification
IRB	Institutional Review Board
mL	Milliliters
ML	Machine Learning
NAA	Non-Advanced Adenoma
NCI	National Cancer Institute
NEG	Negative
NPV	Negative Predictive Value
NSAIDs	Nonsteroidal Anti-Inflammatory Drugs
PPV	Positive Predictive Value
ROC	Receiver Operating Characteristic

SAE	Serious Adverse Event
SAP	Statistical Analysis Plan
SEER	Surveillance, Epidemiology, and End Results
Sn	Sensitivity
SOC	Standard of Care
Sp	Specificity
THC	Tetrahydrocannabinol
WGS	Whole Genome Sequencing

## 1. INTRODUCTION

### 1.1 Background

Colorectal cancer (CRC) is the fourth most frequently diagnosed cancer and the second leading cause of cancer death in the United States. In 2019, an estimated 101,420 new cases of colon cancer and 44,180 new cases of rectal cancer were expected to occur in the United States, and it was estimated that 51,020 people would die from CRC. Screening for persons at average risk for CRC typically begins at age 50, and individuals at average risk have traditionally been defined as those aged  $\geq$  50 years without personal history of inflammatory bowel disease (IBD), adenomas, or CRC; without a family history of CRC or advanced adenomas (AAs); and without symptoms such as rectal bleeding. Registry data from the National Cancer Institute's (NCI) Surveillance, Epidemiology, and End Results (SEER) program indicated an increased incidence of CRC in African Americans prior to age 50 years, which led to the recommendation in 2005 that CRC screening in African Americans begin earlier, at age 45. More recently, epidemiologic reports suggest that the incidence of CRC may be increasing in adults aged  $<$  50 years, leading the American Cancer Society (ACS) in 2018 to recommend considering CRC screening in adults aged 45-49 years. Accordingly, some large commercial payers (e.g., Aetna) have begun providing coverage for CRC screening in adults aged  $\geq$  45 years.

### 1.2 Study Rationale

Despite being widely recommended, more than one-third of age eligible adults remain unscreened for CRC, and cancer is often detected too late for successful treatment, with nearly 60% of CRC cases detected after regional or distant metastases. Currently, there are different methods available for CRC screening, each with their own strengths and weaknesses. Colonoscopy (CS) is highly sensitive, but is inconvenient and invasive, and therefore less appealing. Non-invasive, stool-based approaches are more convenient, but are also less accurate (especially for early-stage disease and precancerous polyps), and require manipulating stools, which can be unpleasant.

Blood-based screening tests for cancer could address some of the aforementioned challenges and supplement or replace existing cancer screening methods. One area of interest is circulating cell-free DNA (cfDNA), which includes both tumor-derived DNA (circulating tumor DNA, or ctDNA) and DNA derived from non-tumor cells, such as hematopoietic and stromal cells. Different screening approaches using cfDNA are being explored, with some proposing that ctDNA-only based tests may enable sensitive and specific early detection of cancer. However, ctDNA generally represents  $\leq$  0.01-1.0% of all cfDNA in early-stage cancer, and even lower in premalignant conditions, thus requiring clinically challenging volumes of blood (e.g., 150-300 mL). These limitations are particularly important in early-stage cancer and precancerous conditions, when the tumor is small, and the shedding of tumor DNA into the blood may be minimal.

An alternative to detection based solely on ctDNA is to look more broadly at cfDNA—both tumor- and non-tumor-derived—and changes that early-stage cancer and precancerous lesions may induce that are detectable in blood. There is growing evidence of interactions between cancerous cells and other cells, including fibroblasts, platelets, and immune cells, especially within the tumor microenvironment. Moreover, exploring signals beyond cfDNA alone, using a multiomics approach that includes additional biomarkers (e.g., proteins, RNA, etc.), may be necessary to achieve the clinical performance required for a blood-based screening test.

In the case of CRC, given its molecular heterogeneity, and biological differences between early- and late-stage disease, detection may be better achieved using a multiomics approach that includes assessing the genome, methylome, transcriptome, and proteome in plasma. For example, proteins such as autoantibodies may enable detection of cancer at an early stage, before the development of clinical symptoms. Conversely, measuring tumor-derived signals from the genome and/or methylome may allow detection of CRC at later stages, when genetic and epigenetic changes are more common. Therefore, combining different approaches may be necessary for detection of all stages of CRC, as well as precancerous lesions. Applying artificial intelligence (AI)/machine learning (ML) enables assessment of disease-related patterns from multiple signals and the identification of relevant, low-dimensional features that generalize to the screening population.

Freenome's early data were based on a single-analyte approach, namely whole genome sequencing (WGS) of cfDNA. In brief, cfDNA alone was assessed for the detection of CRC from 546 individuals with CRC and 271 non-cancer controls (i.e., individuals without a current CRC diagnosis). In this cohort heavily weighted towards early-stage cancer (81% stage I/II), a mean area under the curve (AUC) of 0.92 (95% confidence interval [CI] 0.91-0.93) was achieved, with a mean sensitivity of 85% (95% CI 83-86%) at 85% nominal specificity. More recently, this prototype single-analyte test was expanded to a multiomics test that demonstrated improved performance, achieving 94% sensitivity and 94% specificity for early-stage (I/II) colorectal adenocarcinoma in a multi-center prospective study that included average-risk screening and case-control subjects (n=574) and an analyte training set (n=17) drawn from a statistically-driven subset of AI-EMERGE® (NCT03688906). These findings reinforce our belief that successful early detection of advanced colorectal neoplasia (ACN) will require such an ML-based multiomics approach, which also holds the promise of improving over time as additional real-world testing data becomes available.

Freenome's blood-based, multiomics test (hereafter referred to as "Freenome's test") for CRC screening will enable improved adherence versus current CRC screening efforts, which remain either invasive or stool-based. In addition, use of the test is expected to improve the identification of clinically-actionable disease, defined as disease (i.e., ACN) for which colonoscopic intervention has demonstrated health outcome benefit. This in turn will improve the risk-benefit ratio for patients by increasing the likelihood that those patients directed by the test to undergo a diagnostic CS, with its attendant costs and complications, will benefit from it.

The purpose of the current study is to validate Freenome's test performance and support regulatory approval.

## 2. STUDY OBJECTIVES

### 2.1 Primary

- The primary objectives of this study are to determine the sensitivity (Sn) and specificity (Sp) of Freenome's test for colorectal adenocarcinoma, using screening CS with histopathology as the reference method.

### 2.2 Secondary

- To evaluate the negative predictive value (NPV) of Freenome's test for CRC detection
- To evaluate the positive predictive value (PPV) of Freenome's test for CRC detection
- To evaluate the Sn of Freenome's test for AA

## 3. STUDY DESIGN

### 3.1 Study Overview

This is an international multi-center study for the clinical validation of Freenome's blood test to detect ACN (i.e., CRC and AA). Subjects referred by a healthcare provider (HCP) for a standard of care (SOC) screening CS and providing informed consent are eligible to participate based on the study inclusion and exclusion criteria. Enrollment procedures should be completed within 30 days of signing consent. Should a patient fall outside of the 30-day window, these cases may be escalated to Freenome (or designee) for approval on a case by case basis.

- Subjects who provide informed consent, meet the eligibility criteria and provide the blood sample for this study will be enrolled. Subjects will undergo blood collection and will then have 90 days to complete a SOC screening CS. Maximum time allowed between enrollment and CS will be 90 days. Subjects will have the option to have blood collection done either at the clinical study site or by a study-provided mobile phlebotomy service, in which case the subject can have blood collected in their home or location of preference. Up to 50 mL of blood will be collected from each enrolled subject prior to the bowel preparation for CS. Blood specimens will be used for the clinical and analytical validation of Freenome's test. Blood specimens will be de-identified and sent to Freenome, or a designee, for processing, storage and testing. De-identified specimens and residual specimens will be banked and may be utilized for additional analytical validation testing by Freenome, to improve the current assay in the future, or to develop new assays. Specimens will be used for research purposes only. Since Freenome's test (and any future testing using residual specimens) is currently investigational, results will not be shared with Investigators or subjects.

Study duration is comprised of the time between enrollment and a single study visit for a SOC screening CS and should be no longer than 90 days.

Although no long-term follow-up is planned, subjects may also be contacted by site personnel up to three (3) years following the completion of the study to gather additional information (e.g., any new cancer diagnoses).

### 3.2 Population

[figure not shown]
The study will enroll a representative sample of the population of subjects who are at average risk for the development of CRC and will undergo CRC SOC screening CS from sites across the U.S. and internationally.

### 3.3 Number of Subjects

Approximately 25 ,000 subjects will be enrolled. Of the 25 ,000 subjects, an effort will be made to enroll approximately 70% of subjects in the 65-85 years age group. Enrollment will be stopped when a sufficient number of evaluable cases of CRC have been diagnosed among the study population.

### 3.4 Study Schema

**Figure 1. Study Schema**

 Enrollment procedures should be completed within 30 days of signing consent

### 3.5 Schedule of Assessments

**Table 1. Schedule of Assessments**

Study Procedures	Enrollment	CS Visit (and additional reports)	Notes
Window	30 days	90 days	
Informed Consent	X		Enrollment procedures should be completed within 30 days of signing consent
Evaluation of Inclusion & Exclusion Criteria	X		
Medical History / Demographics	X		
Lifestyle Information	X		Including but not limited to: history of tobacco product use or history of and current information on alcohol consumption and drugs of abuse including recreational and prescribed, including THC.
Concomitant Medications	X		Concomitant medications: (limited to the medications listed in Appendix I ) in the 30 days preceding enrollment
Weight and Height	X		Height and weight to be collected at enrollment; however, patients will have up until the CS visit to complete. Verbally reported measurements are acceptable.
Blood Collection	X		The blood collection should be done within 30 days of signing consent. Should a patient fall outside of the 30-day window, these cases may be escalated to Freenome (or designee) for approval on a case by case basis. The blood collection must be done prior to bowel preparation for the screening CS. Maximum allowed time between blood collection and CS will be 90 days.
Colonoscopy		X	Subjects will be enrolled and will then have 90 days to undergo a SOC screening CS following the blood collection. The CS report must be provided.
Histopathology Report		X	If any lesions are present from the CS report, the accompanying pathology report(s) must be provided.
Imaging Report, Relevant		X	Subjects diagnosed with CRC will require any imaging reports, post-surgery histopathology reports, and/or operative notes required to accurately stage the cancer.

Histopathology, or Operative Notes			
AEs/SAEs	X		Only blood collection related
Central histopathology review		X	H&E slide(s), FFPE blocks or digital image(s) from specific types of polyps resected or biopsied during the screening CS will be required to be sent for central pathology review. Only a subset of polyps will require such review and each site will be sent a list of cases to send for central review.

\*CS: colonoscopy; SOC: standard-of-care; AE: adverse event; SAE: serious adverse event; THC: tetrahydrocannabinol

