## 6. ADVERSE EVENTS

### 6.1 Adverse Event (AE) Definition

Due to the study design and the nature of the blood collection process, the Sponsor does not expect many adverse events (AEs) caused by or related to the blood collection.

Since the screening CS is being performed as SOC and is a routine part of patient care, subjects are at no increased risk because of participation in this study. Thus, while adverse events may be anticipated due to SOC screening CS, they are not regarded as study related.

For the purposes of this study, an AE is defined as any undesirable physical, psychological or behavioral effect experienced during participation in the study that is related to the blood collection for this study. As a result of blood collection, subjects may experience minor pain, discomfort, bruising at the venipuncture site, or lightheadedness.

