### **6.3 Documenting Adverse Events/Serious Adverse Events**

Sites and mobile phlebotomists must observe normal SOC practices to protect the subjects' health and safety during the specimen collection. For SAEs, at each occurrence, the event should be reported to the regulatory body (the Institutional Review Board, IRB) within 1 business day of Investigator knowledge of such event.

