4.1. Intended Use and Study Population

The IUP for this test is adults of either sex, 45 years or older, who are at average-risk for CRC. The study population were adults of either sex ages 45-85, referred by a healthcare professional for CRC screening. Typical subjects presented for medical intervention in a health care setting and met CRC screening criteria for a CS. High-risk individuals and individuals with gastrointestinal symptoms warranting diagnostic or surveillance CS were ineligible. Subjects were considered enrolled after a determination was made by the Investigator that the subject was eligible to participate according to the inclusion/exclusion criteria and understood and signed the informed consent form. No waivers of inclusion or exclusion criteria were granted by the Investigator in this study. Study sites consisted of mostly gastroenterology specialty practice and general health care sites.

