4.4. Colonoscopy

Subjects underwent a SOC bowel preparation followed by SOC screening colonoscopy within 90 days of blood collection (to ensure CRC status has not changed between blood draw and CS). Steps were taken to ensure quality of bowel preparation and colonoscopy were sufficient to evaluate the presence or absence of ACN. In cases where a non-ACN subject did not meet adequate quality colonoscopy, a repeat colonoscopy was allowable within 90 days of blood

This document contains confidential, proprietary information and may not be reproduced or disclosed in whole or in part without written authorization from Freenome Holdings, Inc

		Approval Status	Approved
		Effective Date	5-Jan-2024
Document Number	PL-00052	Current Revision	5
Document Title	Clinical Validation of Freenome's Methylation Blood Test for the Early Detection...		
Document Category	Plan		

collection. Due to the impact that COVID-19 had during this study, sites were occasionally given waivers for completing CS within 120 days after the blood collection. All subjects were required to provide a colonoscopy report, and additionally where applicable, histopathology reports, imaging reports, or operative notes on cancer staging. Although no long-term follow-up is planned, subjects may also be contacted by site personnel for up to 3 years following the completion of the study to gather additional information (e.g., any new cancer diagnosis).

A non-ACN subject who had a bowel preparation rated as less than fair (i.e. poor or inadequate), or an incomplete CS, was considered unevaluable and therefore will be excluded from analysis of all primary and secondary endpoints. An ACN subject who had a bowel preparation rated as less than fair or had an incomplete CS will be included in the analyses. Poor bowel preparation was defined as semisolid stool that could not be suctioned or washed away and < 90% of mucosa was seen. Inadequate bowel preparation was defined as needing repeat preparation for screening. A complete CS was defined as reaching the cecum (reaching the junction between the small and large intestine if the cecum has been resected) or reaching the neo-cecum. Cecal intubation was documented by photographic evidence and/or documentation of cecal intubation.

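### Adverse events are scheduled for collection only at enrolment, with no enquiry after the blood draw, although the definition covers draw-related effects up to the colonoscopy visit

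*Protocol*

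**What the plan says.** Protocol Table 1 (section 3.5) has two procedure columns, Enrollment and CS Visit. The AEs/SAEs row carries a mark in the first and nothing in the second. Its note is "Only blood collection related".

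Section 6.1 defines an adverse event as "any undesirable physical, psychological or behavioral effect experienced during participation in the study that is related to the blood collection for this study". It names pain, discomfort, bruising and lightheadedness as the effects to expect. Section 3.1 describes study duration as the time between enrolment and "a single study visit for a SOC screening CS and should be no longer than 90 days". SAP 4.4 adds that "sites were occasionally given waivers for completing CS within 120 days after the blood collection".

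On what enrolment means, the protocol states "Subjects who provide informed consent, meet the eligibility criteria and provide the blood sample for this study will be enrolled". SAP 4.1 differs: "Subjects were considered enrolled after a determination was made by the Investigator that the subject was eligible to participate according to" the entry criteria and had signed consent. It does not mention the blood sample.

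Section 6.3 asks that each serious event be reported to the IRB "within 1 business day of Investigator knowledge of such event". SAP 5.4 says that every subject in the safety analysis set, meaning those with an attempted draw, will be evaluated for adverse events. SAP 8.5 lists descriptive statistics for them.

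**The concern.** The definition and the schedule do not cover the same time. The definition follows the subject to the colonoscopy. The only scheduled collection point is in the block of procedures that, under the protocol, ends with the blood sample. An effect of the draw can only begin at the draw, and some of the effects that section 6.1 names, bruising in particular, can show after the subject or the phlebotomist has left.

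What is at stake is the reading of the safety table. The SAP promises an evaluation of every subject with an attempted draw. If the schedule is followed as written, the table holds what was seen at the draw plus whatever subjects chose to mention later. A low count could then mean either few events or no enquiry, and the report would give the reader no way to tell which.

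**Working it through.** The documents give no adverse event count, rate or onset time, so there is no figure to reproduce. The check is a comparison of the relevant places.

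1. **Period in which an event counts.** Sections 6.1 and 3.1 together give enrolment to the colonoscopy visit, at most 90 days. Under the SAP 4.4 waivers the colonoscopy could fall up to 120 days after the draw.
2. **Points at which events are scheduled to be collected.** Table 1 gives one, Enrollment. The CS Visit cell is empty.
3. **Where the draw falls.** Under Protocol 3.1 and 5.1, providing the sample is the last of the three conditions for enrolment. Under SAP 4.1 and 5.1, eligibility and consent suffice. Neither definition adds an enquiry after the draw.
4. **Whether the mark might extend beyond the draw.** The Enrollment column has a 30-day window from consent. In the height and weight row, a note expressly allows completion up to the colonoscopy visit. The AEs/SAEs row has no such extension.
5. **Whether another section supplies the enquiry.**
   - Protocol 5.4, the list of eCRF data, does not mention adverse events.
   - Protocol 6.3 sets a rule for serious events only. It starts from the investigator's knowledge and does not say how that knowledge is obtained. It holds mobile phlebotomists to standard practice during collection but does not ask them to tell the investigator of an event.
   - SAP 4.10 gives the DMC the monitoring of serious events related to venipuncture, with no method of ascertainment.
   - SAP 5.4 and 8.5 promise evaluation and description, with no time or method.

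**Result.** The interval with no scheduled enquiry runs from the draw to the colonoscopy: up to 90 days, or up to 120 days for subjects under a waiver. Non-serious events have no stated route into the record during that interval. Serious events have one only if the investigator comes to know of them.

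**The case against.** The best defence is that section 6.1 says which events count and Table 1 says where recording is scheduled, and the two can stand together. That is right. A reader might infer that the two windows contradict each other. The documents do not support this: the row's note does not restrict timing, nothing says that recording stops after the draw, and section 6.3 sets no end date for serious events. What remains is a gap in solicitation.

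A second defence is that operational documents may fill the gap. The protocol refers to a laboratory manual, CRF Completion Guidelines and a DMC charter, none of which is available here. This limits two further inferences. A reader might conclude that adverse event rates after mobile draws are the most understated, but a bruise that appears later is equally unseen after a site draw, the mobile service is provided by the study, and no rates by draw location are given. A reader might also conclude that the DMC's information on serious events was deficient, but its content is left to the charter.

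A third defence is that the matter is small. The expected effects are slight and mostly early, and a question put up to 90 days later depends on recall. This stands, and it sets the grade. It does not remove the gap, because the SAP still promises an evaluation for which no time or method is given.

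**Conclusion.** The point holds as a minor one. Followed as written, the schedule yields adverse event counts less complete than the protocol's own definition calls for. The shortfall falls on non-serious effects that appear after the draw and on serious events that nobody volunteers. It touches the descriptive safety summary only. Sensitivity, specificity, predictive values, the analysis sets and the acceptance criteria are unaffected.

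The proportion of events missed cannot be estimated, because the documents give neither the share that appears after the draw nor the share that subjects would report unprompted. Any percentage would only restate assumed inputs.

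The conclusion assumes that no manual, eCRF instruction or charter outside these documents required an enquiry after the draw. If one did, citing it would close the point.

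**What to change.** Reconcile Table 1, section 6.1 and section 6.3 on when and how adverse events are ascertained:

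- In Table 1, mark AEs/SAEs in the CS Visit column, with one question limited to effects of the study blood draw. The wording should exclude bowel preparation and colonoscopy effects, since section 6.1 does not regard events from the colonoscopy as study related. SAP 4.3 allowed redraws, so the question should cover every study draw.
- In section 6.3, state that mobile phlebotomists relay any adverse event to the site investigator.

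The cost is protocol wording and one eCRF item at a visit the protocol already names. The downsides are more reports of minor bruising and recall over up to 90 days.

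SAP section 4 records that the DMC agreed in March 2022 to close enrolment, so these changes cannot recover data for this study and serve a successor protocol. For this study, the SAP or the clinical study report should state when and how adverse events were ascertained. Unless an instruction outside these documents provided for a later enquiry, it should describe the counts as not actively solicited after the draw. That costs a sentence or two.
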